11.2.8 Immune Endpoints Evaluation

It is expected that pembrolizumab will promote the anti-tumour immune response initiated by the SABR therapy. The working hypothesis is that the induced anti-tumour immune response will be systemic, and this will promote immune surveillance of metastatic lesions. The tumour microenvironment is characterized by an inverse relationship between effector T cells (Teff) and regulatory CD4+ T cells (Treg), tumour associated macrophages (TAM2) and myeloid derived suppressor cells (MDSCs). We expect that SABR+ pembrolizumab (MK-3475) will change this inverse Teff:Suppressor cell balance so that the Teff cells predominate over Tregs and MDSCs. Peripheral blood will be collected before and at intervals during therapy. Alterations in the above immune subsets will be determined by the following (but not limited

to); multi-parameter FACS for T cells (CD3, CD4, CD8, CD45RA, CCR7, CD45Ro), B (CD19), NK (CD3-CD56+CD16+), Treg (CD3,CD4, CD127, FoxP3) and MDSC subsets (CD14+HLADR- and lin-HLADR-CD33+CD15+). We will also examine the immune suppression molecules (TIM3) as well as activation molecules (OX-40) on PB T cell subsets to determine whether these change following treatment with SABR + pembrolizumab.

In the context of renal cancer, therapy-induced tumour-specific T cell responses are difficult to assess as tumour antigens are only partially described. Therefore, we will reveal therapy-induced T cell responses indirectly by examining the TCR repertoire for clonal expansion (next generation sequencing on Illumina).

Lastly, we will examine plasma levels of PD-L1 (sPD-L1) before, during and after therapy to examine whether there is a correlation between patient baseline PD-L1, and whether clinical response correlates with changes in sPD-L1 levels during or after therapy. This will be performed using a commercial ELISA kit assay (see laboratory manual).

11.2.9 Sample Size Calculation

This is a Phase Ib/II study to evaluate the safety profile and efficacy that would then be evaluated in a larger and more appropriately powered future study. The sample size of 30 patients is pragmatic.

The primary objective of the study is to provide a description of the safety profile of the combined SABR and pembrolizumab therapies. Table 8 illustrates different scenarios for grade 3 or 4 AEs rate ranging from 0% to 40% with the respective 95% exact confidence intervals, assuming 30 patients.

Table 8: Confidence Intervals for Adverse Event Rates

Number of patients with grade 3+ AE	Grade 3+ AE rate	95% confidence interval
1	3%	0% - 17%
2	7%	1% - 22%
3	10%	2% - 27%
4	13%	4% - 31%
5	17%	6% - 35%
6	20%	8% - 39%
7	23%	10% - 42%
8	27%	12% - 46%
9	30%	15% - 49%
10	33%	17% - 53%
11	37%	20% - 56%
12	40%	23% - 59%

Expected toxicities related to the pembrolizumab treatment are listed in the Investigator's Brochure. Therefore, immune related events such as hypothyroidism, pneumonitis, and colitis are expected. They should occur in <5%. Pneumonitis and colitis are considered to be the most serious but are rare events. Immune events and other events of clinical interest will be monitored for closely in this study, with early stopping rules as detailed below.

Recruitment will occur over a two-year period. An interim analysis after 15 patients completes 6 months of follow-up will be conducted for presentation purpose. The final analyses will be at the completion of 12 months after the last participant has completed SABR treatment.

11.2.10 Early Termination Criteria

A Safety Monitoring Committee (SMC) will be formed prior to trial activation, to review the information from the safety analyses performed after the first 12 patients have completed SABR and 12 weeks of pembrolizumab treatment. The Trial Management Committee (TMC), will have responsibility for any final decisions about protocol stopping or modification.

Consideration of the cessation of participant accrual will occur if an unacceptable rate of toxicity is detected. The expected rates of grade 3+ pneumonitis and colitis are expected to be less than 5%. Thus, after 12 patients have completed 12 weeks of follow up following treatment, consideration by the SMC will be given to stopping the trial if any of the following is observed:

- a. The number of \geq grade 3 pneumonitis toxicity events is ≥ 2 (*expected rate of <5%*)
- b. The number of \geq grade 3 bowel toxicity events is ≥ 2 (*expected rate of <5%*)

If the true grade 3+ pneumonitis and bowel toxicities rates are 5%, the probability of early stopping due to unacceptable toxicity rate is 22% assuming the two types of toxicities are independent.

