7.7.3 Treatment Related Toxicity

Toxicity data was available for all ten studies. Grade 3 to 4 toxicities ranged from 0% to 4%. There were a total of two treatment related deaths. One patient who had a large metastatic

lesion (516cc) in the lung close to the pleura, died 10 weeks after receiving SABR (48Gy in 4 fractions). This patient was admitted to hospital with electromechanical dissociation (EMD). The second mortality was due to a fatal gastric haemorrhage 4 months after treatment for a metastasis in the pancreas adjacent to the stomach and duodenum. No details regarding radiotherapy dose was available in this patient.

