7.10 Summary of Risks and Benefits

SABR involves highly hypofractionated radiotherapy given as an ablative treatment. While there is extensive literature suggesting that it is safe and has low rates of major toxicities, such studies have tended to have small numbers and relatively short follow up given most patients succumb to their metastatic disease. Thus, by combining a short course of immunotherapy after SABR, we postulate that this will result in a lower likelihood of patients succumbing to further disease recurrence.

The risk of SABR treatment depends on the exact anatomical site of the oligometastatic disease irradiated. There is a low but not negligible risk of radiation pneumonitis, bone fractures, radiation enteritis, skin fibrosis, renal impairment and proctitis. There is an exceedingly low risk of transverse myelitis.

SABR is thought to provide long-term local control of known oligometastatic sites of cancer. It also provides good and durable pain relief for painful metastases. It is postulated that SABR to sites of oligometastatic or oligoprogressive renal cell carcinoma, in selected patients, may prolong survival. Clearly studies that determine whether a survival benefit occurs with such treatment remain to be conducted and reported.

It is acknowledged that patients may have received previous radiotherapy to an area where SABR is to be delivered in this protocol (equivalent dose of 30 Gy in 10 fractions). Due to the increased dose that is received in this instance, there is an increased risk of radiation toxicity in these patients. This potential increased level of risk has been highlighted in the patient information and consent form and must be discussed in each instance prior to informed consent. Patients who have received more than this RT equivalent dose schedule to an area planned for further SABR treatment are not eligible for this study.

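### The only numeric toxicity boundary is applied at one look after 12 patients, timed in two ways, and nothing requires the SMC to meet when the second qualifying event occurs

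*Combined protocol and SAP*

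**What the plan says.** Section 11.2.9 announces that "Immune events and other events of clinical interest will be monitored for closely in this study, with early stopping rules as detailed below". The rule follows in section 11.2.10, which dates the review twice:

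- The SMC is formed to review "safety analyses performed after the first 12 patients have completed SABR and 12 weeks of pembrolizumab treatment".
- In the next paragraph, "after 12 patients have completed 12 weeks of follow up following treatment, consideration by the SMC will be given to stopping the trial".

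The boundary has two limbs, both for grade 3 or higher: (a) "grade 3 pneumonitis toxicity events is ≥ 2" and (b) "grade 3 bowel toxicity events is ≥ 2". The reference is given as follows: "The expected rates of grade 3+ pneumonitis and colitis are expected to be less than 5" per cent. If both true rates are 5% and the two toxicities are independent, the section puts the probability of early stopping at 22%.

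Section 11.2.10 contains no running count, no accrual pause, no trigger for an unscheduled SMC meeting and no boundary after the first 12 patients. The only other interim analysis, when 15 patients reach 6 months, is for presentation only (sections 11.2.9 and 13.5).

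**The concern.** Safety is the primary objective. Once two of the first 12 patients have had grade 3+ pneumonitis, limb (a) is met and the remaining results among the 12 cannot undo it. As written, the SMC's consideration still waits until all 12 have completed the 12 weeks, and patients can be registered and treated in the meantime. The length of that wait depends on which of the two timings applies.

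Two further points affect how the rule is read.

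- With 12 patients a single look can miss a clearly raised rate, and no number governs what follows.
- The reference rate is for colitis, whereas limb (b) counts bowel toxicity. The preceding text in section 11.2.9 concerns toxicities of pembrolizumab, while section 7.10 says of SABR that "There is a low but not negligible risk of radiation pneumonitis, bone fractures, radiation enteritis" can occur. A reader cannot tell whether the 5% behind the 22% is meant to cover drug and SABR together.

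**Working it through.** **Inputs.** 12 patients, a boundary of 2 per limb and a 5% reference rate (11.2.10); 30 evaluable patients (8.2); two-year recruitment (11.2.9); radiotherapy within 4 weeks of registration (9.1.2); cycle 1 at 5 days after SABR (9.1.18); 8 cycles, 3 weeks apart (9.1.19). Uniform accrual is my assumption, as is counting registered patients as evaluable. A month is 30.44 days.

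**1. The plan's own figure.** For one limb, P(X ≥ 2) = 1 − (1−p)^12 − 12p(1−p)^11. At p = 0.05 this is 1 − 0.5404 − 0.3413 = 0.1184. For either limb, 1 − (1 − 0.1184)² = 0.2227. The stated 22% is reproduced.

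**2. Sensitivity of the single look.**

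| True rate | One limb met | One limb not met | At least 2 more affected among patients 13-30 |
|---|---|---|---|
| 5% | 11.8% | 88.2% | 22.6% |
| 10% | 34.1% | 65.9% | 55.0% |
| 15% | 55.7% | 44.3% | 77.6% |
| 20% | 72.5% | 27.5% | 90.1% |

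The last column is the same formula with 18 patients in place of 12. At 20%, four times the reference, the toxicity passes its own limb 27.5% of the time.

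**3. When the look falls.** Accrual is 30/24 = 1.25 patients per month, so patient 12 registers at 12/1.25 = 9.6 months.

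- *12 weeks of pembrolizumab:* 9.6 + (0 to 0.92) to SABR + 0.16 to cycle 1 + 2.76 = 12.5 to 13.4 months; × 1.25 = 15.7 to 16.8, about 16-17 registered.
- *12 weeks after SABR* (one reading of the second timing): 12.4 to 13.3 months, 15.4 to 16.6 registered.
- *12 weeks after cycle 8* (the other reading): add 7 × 21 = 147 days, or 4.83 months, to the first case. This gives 17.3 to 18.3 months and 21.7 to 22.8, about 22-23 registered.

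**4. Where the second event falls.** P(second affected patient is number j) = (j−1)p²(1−p)^(j−2) for j = 2 to 12. Given that the limb is met, the mean of j is 8.3, 7.9 and 6.9 at true rates of 5%, 10% and 20%.

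**5. Effect of acting at the second event.** Reaching 2 affected patients at any point within 12 is the same event as 2 or more of 12. With the same patients and the same counting period, the probabilities stay at 11.8% per limb and 22.3% for either.

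**The case against.** The best reply is that this is a 30-patient descriptive study with several layers of safety oversight. Section 9.6.1, criterion 3, allows early termination for the incidence or severity of adverse drug reactions. Section 11.2.10 has a general sentence on ceasing accrual for unacceptable toxicity. Section 13.9 gives the SMC a remit over toxicity and serious events, section 13.8 lets the TMC act on information beyond the interim analyses, and section 10.8.5 requires rapid reporting of serious events, which are then assessed one by one. This stands, and it limits the point. A reader might infer that patients 13-30 have no rule at all; the documents do not support that. What they lack is a numeric rule or a scheduled SMC look. None of these safeguards has a threshold, a meeting frequency or a link to the count of two, and grade 3 alone is not among the criteria for a serious event.

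Three other stronger readings also fail.

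- **That the 22% is wrong, or that SABR raises false stopping to 29-50%.** Those figures come from true rates of 6% and 9% on both limbs: 1 − (1 − 0.1595)² = 29.4% and 1 − (1 − 0.2948)² = 50.3%. The added 1 to 4 points would have to be drawn from section 7.7.3, where "Grade 3 to 4 toxicities ranged from 0% to 4" per cent refers to all grade 3-4 toxicity across studies, not to pneumonitis or bowel toxicity. Putting 4 points on each limb makes 8 in total, above that maximum. Nor is a flag at 6-9% false, since such a rate exceeds the expected level. Section 11.2.10 conditions its 22% on the true rates being 5%.
- **That about nine exposures are avoidable**, taking patient 7-8 from 16-17. Patient order is not calendar time. The saving depends on when events begin, which the documents do not give.
- **That a second look at 24 patients is needed.** Patient 24 registers at 24/1.25 = 19.2 months, so on the first timing the look falls at about 22.1 to 23.0 months with 28-29 of 30 registered. With a boundary of 4 of 24 per limb, one-limb detection rises from 56% to 65% at 15% and from 73% to 83% at 20%, but almost no one is spared enrolment.

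**Conclusion.** The point holds for the formal stopping rule. The boundary can be crossed well before anything obliges the SMC to consider it, and section 11.2.10 gives two timings for that consideration. By then about 16-17 patients are registered, or about 22-23 if the 12 weeks run from cycle 8; both counts rest on uniform accrual. The single look meets a limb only 34%, 56% and 73% of the time at true rates of 10%, 15% and 20%, and no number applies to the remaining 18 patients. How many exposures earlier action would prevent cannot be calculated from the documents.

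The 22% is correct for the rule as written. That the 5% is a drug-only figure is an inference from section 11.2.9, because section 11.2.10 names no source. The mismatch between colitis and bowel toxicity is in the text. This change should be made because it is nearly free; it does not show the trial to be unsafe.

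**What to change.** 1. State in section 11.2.10 that the SMC is convened as soon as a second patient among the first 12 has a qualifying event of the same type. Count patients, as the 22% does. The stated probability does not change. The cost is a sentence in the SAP and a possible ad hoc meeting.
2. Reconcile the two timings of the 12-patient look, and define the start of the 12 weeks. Which timing applies is for the sponsor and the SMC to decide.
3. Use the same event for the reference rate and limb (b), and state that the 22% refers to the total rate from pembrolizumab and SABR together. This is wording only.

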Any serious adverse event, or follow up to a serious adverse event, including death due to any cause other than progression of the cancer under study that occurs to any participant from the time the consent is signed through 90 days following cessation of pembrolizumab treatment, or the initiation of new anti-cancer therapy, whichever is earlier, whether or not related to protocol treatment, must be reported within 24 hours to the Sponsor and within 2 working days to Merck Global Safety.

Additionally, any serious adverse event, considered by an investigator who is a qualified physician to be related to protocol treatment that is brought to the attention of the investigator at any time outside of the time period specified in the previous paragraph also must be reported immediately to the Sponsor and to Merck.

SAE reports and any other relevant safety information are to be forwarded to the Merck Global Safety [contact].

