10.8.5.1 Serious Adverse Event Reporting

Trial Sites/Investigators

All SAEs that occur from the time a participant has signed consent for the Trial to within 90 days of the final protocol-specified treatment, intervention or procedure or the initiation of new anti-cancer therapy, whichever is earlier, are required to be reported to the Sponsor whether or not considered related to the treatment under investigation.

The **Principal Investigator (PI)** or delegate must:

- Determine whether an AE is 'Serious'
- For SAEs, the PI or delegate must then ascertain the suspected cause
- Ascertain severity
- Record the SAE in the patients' medical records and submit an SAE form.
- Report the SAE on the Trial SAE form to Sponsor and Merck no later than 24 hours after becoming aware of the event. The investigator may be requested by the Sponsor or Merck to provide or obtain specific additional follow-up information in an expedited fashion for the purpose of safety assessment

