10.8.5.2 Sponsor Responsibility

The Sponsor is responsible for:

- Implementing and maintaining a suitable recording system to record information from all SAEs received from Trial Sites.
- Ensuring that the Coordinating Principal Investigator (CPI) is notified of each SAE to enable the SAE to be assessed by the CPI and any other appropriate reviewers for nature (expected/unexpected), causality and whether the TGA needs to be notified of the SAE.
- Notifying the TGA (Australia) in accordance with the regulatory authority's detailed guidance of any SUSARs that are fatal or life threatening as soon as possible but no later than 7 days after the site gained first knowledge of the event. Incomplete reports must be completed and forwarded as soon as possible within 8 additional calendar days. All

other SUSARs should be reported to the TGA within 15 days after the site gained first knowledge of the event.

- Considering information provided by (non-serious) adverse event data.
- Informing each trial site of new information arising from serious and non-serious adverse events and adverse drug reactions that may affect the conduct of the Trial, or the rights, interests, safety or wellbeing of trial patients.
- Notifying the TGA of any significant issue that has arisen from analysis of overseas reports or action that has been taken by another country’s regulatory authority within 72 hours of first knowledge.

SAEs must be reported by completing the sponsor Trial SAE form and FAXING or Emailing to the following:

Sponsor	Email: [contact]
Merck Global Safety	[contact]

SAE forms are required at the following points:

Initial Report	Within one working day/24 hours of discovery or notification of the event. If the reporting of an SAE is delayed by more than 24 hours, an explanation must be provided. This report may be signed by a clinician who is not the treating doctor.
Incomplete Reports*	If all details are not available at the time of the initial report a completed report must be sent within the next 10 days.
Updated Report	If the event is not resolved (or is ‘on-going’) at the time of the initial report, the ‘UPDATE: Outcome of Event’ section’ of the SAE Form must be completed and the form submitted to BaCT and the SAE reviewer as soon as the event is resolved (with or without sequelae) or if death has occurred.

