*The Investigator is ultimately responsible for reporting the SAE and must sign the final SAE report(s). Should this Investigator not be available to sign the initial SAE form within the 24-hour period, a comment to this effect must be written on the form and the form signed by the clinician attending to the patient at the time and faxed to the Sponsor. The investigator must sign the SAE form as soon as possible and re-fax to the Sponsor

The Investigator at the Trial Site is responsible for determining the local SAE reporting requirements of the responsible HREC and subsequently notifying the HREC of SAEs as required.

All participants with serious adverse events must be followed up for outcome.

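### One treatment-related death can meet neither stopping trigger in section 11.2.10, and no section requires the Safety Monitoring Committee to review it promptly

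*Combined protocol and SAP*

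**What the plan says.** Section 11.2.10 sets up an SMC "to review the information from the safety analyses performed after the first 12 patients have completed SABR and 12 weeks of pembrolizumab treatment". At that point, "consideration by the SMC will be given to stopping the trial if any of the following is observed": (a) at least two pneumonitis events of grade 3 or higher, or (b) at least two bowel toxicity events of grade 3 or higher. Each type is expected in fewer than 5% of patients. At true rates of 5%, the section states that "the probability of early stopping due to unacceptable toxicity rate is 22% assuming the two types of toxicities are independent". A more general sentence in the same section says that stopping accrual will be considered if the toxicity rate proves unacceptable. It names no event type, count or date.

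Deaths are handled elsewhere as serious adverse events (SAEs):

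- **Section 10.8.5.** An SAE, including a death not due to progression, "must be reported within 24 hours to the Sponsor and within 2 working days to Merck Global Safety". Related SAEs outside the standard window must also be reported immediately.
- **Section 10.8.5.1.** The standard window runs from consent to "within 90 days of the final protocol-specified treatment, intervention or procedure or the initiation of new anti-cancer therapy", whichever comes first.
- **Section 10.8.5.2.** The sponsor notifies the coordinating principal investigator (CPI) "to enable the SAE to be assessed by the CPI and any other appropriate reviewers for nature (expected/unexpected), causality". The regulator is told of "any SUSARs that are fatal or life threatening as soon as possible but no later than 7 days". The site investigator is responsible for "determining the local SAE reporting requirements of the responsible HREC and subsequently notifying the HREC of SAEs as required".
- **Section 9.6.1, item 3.** The incidence or severity of adverse drug reactions can end the trial.
- **Sections 13.8 and 13.9.** The SMC's remit includes SAEs. The Trial Management Committee (TMC) may act on SMC recommendations that rest on information outside the planned analyses.

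The analysis after 15 patients (sections 11.2.9 and 13.5) is for presentation only and is not an SMC review.

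**The concern.** Safety of the combination is the primary objective, and section 7.11 accepts that the overlapping toxicities are not fully understood. Both numeric triggers need two events of one named kind. A fatal pneumonitis adds one to trigger (a). A fatal event that is neither pneumonitis nor bowel toxicity adds nothing to either.

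The committees differ in make-up. The SMC has two independent oncologists alongside the study statistician. The TMC, which takes the final decision, consists of the trial's own investigators, physicist, statistician and manager. A trial could therefore follow the plan exactly, have a related death, and go on registering patients before anyone independent of the trial team within its own safety structure had reviewed it. A death before the 12-patient look might wait for that look. A death after it has no scheduled SMC review at all.

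The section 7.7.3 review of SABR (stereotactic radiotherapy) records two treatment-related deaths: one after treatment of a large lung metastasis, and one gastric haemorrhage four months after treatment. Neither would clearly count towards a trigger, and as a single event neither could meet one.

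**Working it through.** **1. The plan's own figure.** Inputs from section 11.2.10: 12 patients, threshold 2, true rate 5% for each toxicity, independence.

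- One trigger: P(X ≥ 2 | n = 12, p = 0.05) = 0.1184.
- Either trigger: 1 − (1 − 0.1184)² = 0.2227.

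The stated 22% reproduces.

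**2. Chance that neither trigger is met, given one death among the first 12.** This needs no assumed death rate. It assumes independent patients and toxicities and at most one event of each type per patient. The 5% is the plan's ceiling; the 2% is my assumption.

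*Fatal pneumonitis.* Trigger (a) stays unmet if none of the other 11 patients has grade 3+ pneumonitis. Trigger (b) stays unmet if there are fewer than two bowel events in 12. The formula is (1 − p)¹¹ × P(X < 2 | 12, p).

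*Fatal event of another type.* Both counts must stay below two: P(X < 2 | 12, p)².

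| True rate of each toxicity | Fatal pneumonitis | Fatal event of another type |
|---|---|---|
| 5% | 0.5688 × 0.8816 = 0.501 | 0.8816² = 0.777 |
| 2% | 0.8007 × 0.9769 = 0.782 | 0.9769² = 0.954 |

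**3. When the look falls.** Inputs: 30 patients in 24 months, taken as even accrual (1.25 per month) with every registered patient evaluable. The 12th patient is registered at 12 / 1.25 = 9.6 months. First pembrolizumab is 5 days after SABR, and 12 weeks is 84 days. For the later end of each range I add the permitted 4 weeks from registration to radiotherapy and 21 days to treat all lesions (49 days). A month is 30.4 days, with no dose delays.

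Section 11.2.10 words the timing in two ways: after 12 weeks of pembrolizumab, and after 12 weeks of follow-up once treated. If the second means after all 8 cycles, the last dose is 7 × 21 = 147 days after the first.

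| Reading | Days after registration of the 12th patient | Month of look | Registered by then |
|---|---|---|---|
| 12 weeks of pembrolizumab | 5 + 84 = 89, to 138 | 12.5 to 14.1 | 15.7 to 17.7 |
| 12 weeks after all 8 cycles | 5 + 147 + 84 = 236, to 285 | 17.4 to 19.0 | 21.7 to 23.7 |

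**4. Illustration of how often a death trigger might be used.** Sections 7.7 and 7.7.3 give 2 related deaths in 389 SABR patients: 0.51%, exact 95% CI 0.06% to 1.8%. The chance of at least one death is 1 − (1 − 0.00514)ⁿ: 0.060 for n = 12 and 0.143 for n = 30.

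Adding a death trigger to (a) and (b), with deaths independent of the two toxicities at 5%:

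- deaths in the first 12: 1 − 0.7773 × (1 − 0.060) = 0.269;
- deaths in all 30: 1 − 0.7773 × (1 − 0.143) = 0.334.

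Across the interval for the death rate these run from 0.229 to 0.378 and from 0.237 to 0.555. They are not upper bounds, because deaths from pembrolizumab or conventional radiotherapy are not counted. Positive dependence, such as a death from pneumonitis, would lower them.

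**The case against.** The strongest reply is that the protocol already deals with a death. The sponsor hears within 24 hours, the CPI assesses it with other reviewers, a fatal unexpected related reaction reaches the regulator within 7 days, and the ethics committee is told as locally required. Section 9.6.1 allows termination on severity alone, without a count or a date. The general sentence in section 11.2.10 is not confined to pneumonitis and bowel toxicity, and the SMC's remit covers SAEs with no time limit. All of that stands. A reader might infer that the trial would have to carry on regardless after a death, or could not act on one; the documents do not support that. What they leave open is narrower: every one of these provisions reports or permits, and none requires prompt SMC review.

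The percentages in step 2 are also conditional. They take the death as given, and in large part restate that one is less than two. That is fair: they show how weak the numeric triggers are as a backstop, not how likely a death is. The 2/389 rate comes from mixed regimens and targets without pembrolizumab, so it serves only as illustration.

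Finally, holding registration after one possibly related death is a real accrual rule and not merely a change of wording. That also stands, and it is counted as a cost below.

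**Conclusion.** The gap is real and limited. A single related death can leave both numeric triggers unmet: 50% to 78% of the time for a fatal pneumonitis in the first 12, and 78% to 95% for another fatal event, at toxicity rates of 5% and 2% and under independence. The only dated SMC review comes at about month 12.5 to 14 with 16 to 18 patients registered, or month 17 to 19 with 22 to 24, depending on how section 11.2.10 is read and on even accrual.

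Two further inferences should be resisted. The 22% is not an error; it describes triggers (a) and (b) correctly. Nor does the gap mean that one death should stop the trial: the case is for mandatory review, not for an automatic stop. This is a cheap patient-safety improvement to a plan that otherwise permits the right response.

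**What to change.** Add to section 11.2.10:

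*(c) Any death judged possibly, probably or definitely related to SABR, conventional RT or pembrolizumab, at any time from first protocol treatment to the end of study follow-up, is referred to the SMC for expedited review. While accrual is open, no further patient is registered until the SMC has reviewed it, and the SMC advises on continued dosing.*

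The clause should not be cut off at 90 days. A patient who stops after one dose would leave a 90-day window about 95 days after SABR (5 + 90), and after two doses at about day 116 (5 + 21 + 90). Either is too early for a haemorrhage at four months. Section 10.8.5 already requires related SAEs outside its window to be reported, so no new data collection is needed.

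Keep the 22%, labelled as the chance that (a) or (b) is met at the 12-patient look. State which of the two timings for that look is meant.

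The cost is a possible short accrual pause and one extra SMC meeting per related death. On the SABR-only illustration, the chance of at least one review trigger rises from 22% to about 27% counting deaths in the first 12, or 33% counting deaths in all 30. The true figures could be higher, because deaths from the drug and from conventional radiotherapy are left out.
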